### **Procedures Done for Research Purpose**

- Comparison Group (CleanSweep™ Closed Suction System)
  - In addition to suctioning performed as per department policy, ETTs cleaned with balloon sweeping technology with every respiratory therapist suctioning.
- Standard Group (Standard in-line suction device)
  - Suctioning performed as per department policy

### **Subject Population**

Two hundred and seventy-two orally intubated, adult patients  $\geq 18$  year of age will be enrolled.

Inclusion criteria:

- Age  $\geq 18$  y/o
- Orally intubated with endotracheal tube
- Mechanically ventilated  $< 24$  hours prior to enrollment

Exclusion criteria:

5.15.2020

- Age < 18 y/o
- Tracheostomy tube
- Extracorporeal membrane oxygenation
- Transfer from outside hospital with more than 24 hours of mechanical ventilation

### **Recruitment and Consent Procedures:**

- Recruitment will be based on the inclusion and exclusion criteria.

### **Compensation:**

- There will be no compensation provided to participants for participation in this study.

### **Risk to subject:**

- Risks include potential desaturation during ETT scraping. To prevent or lessen the possibility of oxygen desaturation, the patient will be preoxygenated with 100% oxygen for 1 to 2 minutes before ETT cleaning is performed.

### **Special Precautions:**

- All study material will be coded to de-identify participants and a separate list will be kept with the participant's ID and name.
- All identifiers will be removed prior to analysis. Study subjects will not be re-identified or contacted after data collection is complete.

### **Confidentiality:**

- The study investigators, along with the IRB, will have access to the individual participant's results. Neither names nor personal information will be recorded or included in the data analysis. The investigators will strictly adhere to IRB guidelines to ensure that participant's confidentiality is maintained.

### **Plans for Data Analysis:**

- **Calculated sample size.** Based on previous institutional data, length of mechanical

ventilation is approximately 6.3 days with a standard deviation of 3.64. Effect is estimated at a 20% reduction in the length of mechanical ventilation ( $6.3 \times .20 = 1.26$  days). Standardized effect size would be 35% ( $1.26/3.64$ ). Setting alpha at 0.05 and power of .80 with standardized effect size of 0.35 would require 136 patients in each group or 272 total number of subjects. Estimated completion would be 18 to 24 months.

- Data for each patient will be recorded in REDCap, a secure web-based database. Descriptive and inferential statistics were calculated from the information collected from patients' charts. Patients were divided into two groups based on randomization. Each group's time to first successful SBT and length of mechanical ventilation outcomes will be compared using an independent T-test if the data is normally distributed. Ventilator-associated conditions and infection related ventilation associated complications rates for both groups will be compared using Chi-Square analysis. Level of significance will be set at  $p < 0.05$ .

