## Introduction

Mechanical ventilation (MV) is utilized when the patient's work of breathing (WOB) exceeds their capacity to do that work, with risk of respiratory muscle failure. Approximately half of the time spent on MV is on the process of weaning and discontinuing this support as soon as possible. The focus on MV liberation is due to the associated complications, including an increased risk of pneumonia. The weaning process can be challenging and is categorized as simple, difficult, or prolonged in regards to weaning success. Difficult to wean patients are categorized as such by failing their initial spontaneous breathing trial (SBT) and require up to three subsequent SBTs to pass; or up to seven days to completely wean from mechanical ventilation after the initial SBT. The difficult and prolonged to wean groups account for approximately 31% of the patients weaned from mechanical ventilation. It has been reported that these groups combined account for a 25% mortality rate. Others reported the incidence and mortality related to these weaning categories in a large cohort study on 257 patients, where the simple to wean group represented 59% with a mortality rate of 13%, the difficult to wean group represented 26% of patients with a 9% mortality rate, and the prolonged weaning group represented 14% of the group with a 32% mortality rate.

Evidence-based guidelines were published over a decade ago to help guide the weaning process and are still applicable today. Once the acute underlying disease process associated with the initiation of mechanical ventilation has improved and spontaneous breathing efforts are evident, patients are assessed for their readiness to wean and extubate. Physiologic signs including respiratory pattern, gas exchange, hemodynamic stability, body temperature, hemoglobin levels, and mental status are all used to determine the discontinuation of mechanical ventilator support. Patients are then assessed for discontinuation of mechanical ventilation by

using a SBT. A SBT involves a low level of mechanical ventilatory support or a T-piece attached to the endotracheal tube. The methods of performing a SBT are variable and the recommendations from the literature are inconsistent on this topic. The main purpose of the SBT is to mimic spontaneous breathing to assess a patient's ability to breathe without the assistance of a mechanical ventilator.

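### The 80% power with 272 patients is for length of ventilation with every patient analysed; the primary outcome was not sized, and its t-test has no value for patients who never pass an SBT

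*Combined protocol and SAP*

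**What the plan says.** Under Plans for Data Analysis, the sample size starts from institutional data on one variable: length of mechanical "ventilation is approximately 6.3 days with a standard deviation of 3.64" (days). The target difference is on the same variable: "Effect is estimated at a 20% reduction in the length of mechanical ventilation", which is 1.26 days. The paragraph then fixes the error rates, "Setting alpha at 0.05 and power of .80 with standardized effect size of 0.35", and concludes that this "would require 136 patients in each group or 272 total number of subjects".

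Subject Population sets enrolment at the same figure, "Two hundred and seventy-two orally intubated, adult patients", and Experimental Design and methods repeats n = 272. No section mentions an allowance for death, withdrawal, transfer or missing outcomes.

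Specific Aims names time to first successful SBT as the primary aim and lists length of ventilation among the secondary aims. The analysis paragraph plans an independent t-test for both outcomes if the data are normally distributed. It names no alternative test, and it does not say what happens to a patient with no successful SBT.

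**The concern.** A t-test needs one number per patient. A patient who dies on the ventilator, is withdrawn, or is transferred before passing an SBT has no time to first success. Followed as written, the primary comparison runs on those who passed, which has two consequences.

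- **Precision.** The number analysed falls below the number enrolled, and the plan makes no stated provision for this.
- **Bias.** Passing an SBT happens after randomisation and may itself be affected by the suction system. Comparing only those who passed is no longer a comparison of the randomised groups.

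Such losses are foreseeable. Patients are enrolled within 24 hours of the start of ventilation, and the Introduction cites a weaning cohort with appreciable mortality, in which "the prolonged weaning group represented 14% of the group with a 32% mortality rate". The only power figure in the plan belongs to a different outcome, so a reader of a null primary result would have no sound basis for judging how informative it is.

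**Working it through.** **Inputs, from Plans for Data Analysis.** Mean 6.3 days, SD 3.64, reduction 6.3 × 0.20 = 1.26 days, alpha 0.05, power 0.80, 136 per group. The standardized effect is 1.26/3.64 = 0.346, which the plan rounds to 0.35. Sidedness is not stated. Two-sided is assumed, because one-sided testing needs only about 102-104 per group and does not lead to 136.

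**Step 1: reproduce the plan's figure.** For two equal groups, n per group = 2(z₀.₉₇₅ + z₀.₈₀)²/d² = 2(1.960 + 0.842)²/d² ≈ 15.70/d².

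- d = 0.346 (unrounded): 15.70/0.1198 = 131.0, rounded up to 132. The exact t-test also gives 132.
- d = 0.35: 15.70/0.1225 = 128.1, rounded up to 129. The exact t-test gives 130.

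The plan's 136 is within 3% of 132 and slightly conservative. Two unstated adjustments would give exactly 136 from d = 0.35: a rank-test efficiency factor (129.1 × π/3 = 135.2, rounded up) and a 5% dropout inflation (129/0.95 = 135.8, rounded up). The plan mentions neither.

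**Step 2: how much loss the margin absorbs.** With d = 0.346, 1 − 132/136 = 2.9%. With d = 0.35, 1 − 129.1/136 = 5.1%. So 80% survives a loss of about 3-5%.

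**Step 3: power if a fraction x has no SBT time and is dropped.** The number analysed per group is 136 × (1 − x), with a two-sided t-test at 0.05. The length-of-ventilation effect is carried over to the SBT outcome as an assumption, since the documents give no other. The values of x are also assumptions.

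| Loss x | Analysed per group | Power, d = 0.35 | Power, d = 0.346 |
|---|---|---|---|
| 0% | 136.0 | 82.0% | 81.2% |
| 5% | 129.2 | 80.0% | 79.2% |
| 10% | 122.4 | 77.9% | 77.0% |
| 20% | 108.8 | 72.9% | 72.0% |
| 30% | 95.2 | 67.1% | 66.1% |

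**Step 4: what the Introduction says about loss.** Weighting the cited cohort's mortality by group share gives 0.59 × 13 + 0.26 × 9 + 0.14 × 32 = 7.7 + 2.3 + 4.5 = 14.5%. This is mortality among patients in weaning categories. It is not the proportion who never pass an SBT.

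**The case against.** A reader might infer that the plan promises 80% power for the primary t-test and fails to deliver it. The documents do not support that. The 80% is stated for length of ventilation, and a patient who dies still has a number of ventilated days, so deaths do not reduce the sample for the outcome that was sized. There is no stated primary power to fall short of.

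A reader might also take 14.5% as the loss rate and conclude that power is about 75%. That goes too far as well. The Introduction describes difficult-to-wean patients as needing further SBTs in order to pass, and simple weaning implies passing the first. On that reading, most deaths in those two groups (7.7 + 2.3 = 10 of the 14.5 points) follow a passed SBT and have an outcome value. Only the prolonged group's 4.5 points might lack one. At 4.5% loss, power is 80.2% (d = 0.35) or 79.4% (d = 0.346), essentially the stated figure. Deaths before weaning begins would add to the loss, but the documents give no rate for them.

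Finally, 136 is not the bare minimum: the t-test needs 130 to 132 per group, so there is a small margin.

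All three objections stand, and they limit the size of the claim. They do not answer the remaining point: the primary outcome has no sizing and no rule for patients without a success, and its t-test would be confined to those who succeed.

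**Conclusion.** The point holds in a limited form. The stated 80% applies to length of mechanical ventilation with all 272 patients analysed. Time to first successful SBT was not sized, and the planned t-test cannot use patients who never pass an SBT.

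The size is conditional. With the length-of-ventilation effect carried over, complete data give 81-82% power, and 80% is lost once more than about 3-5% of patients have no success. This rests on two-sided testing, equal loss in both groups, and an effect and SD for the SBT outcome that match those for length of ventilation in standardized terms. The last assumption is untested, so true power for the primary outcome could lie outside the tabulated range. Any single restated figure would therefore be false precision.

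The loss of power is moderate. The bias from analysing only those who pass is the more serious consequence, and enrolling more patients would not remove it.

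**What to change.** In Plans for Data Analysis:

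1. Replace the primary t-test with a time-to-event comparison of first successful SBT in all 272 randomised patients. Count death before success as a competing event, and censor other patients without a success at last follow-up. Comparing cumulative incidence with Gray's test is one suitable form. State the time origin and the end of follow-up.
2. Say that the 80% power refers to length of mechanical ventilation with complete data.
3. Give power for the new primary analysis as a range over assumed rates of no successful SBT, with the assumed effect stated. It should be calculated for that method, because the t-test figures above do not transfer directly.

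No extra enrolment is needed. The cost is a few sentences, slightly more analysis work, recording the date of death or last follow-up for patients without a success, and a stated power that may look less favourable than 80%.

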## Specific Aims

The primary aim of this study is to evaluate the CleanSweep™ Closed Suction System on time to first successful SBT in mechanically ventilated patients in the medical intensive care unit.

Secondary aims of this study are to evaluate the use endotracheal tube sweeping compared to closed suctioning effect on length of mechanical ventilation, length of ICU stay, length of total hospital stay, and occurrence of ventilator-associated events.

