## **Experimental Design and methods**

This is designed as a prospective, randomized control trial, in a large, urban, academic

medical center. This study will include mechanically ventilated patients (n = 272) in the medical intensive care unit (MICU) and adult intensive care unit at Rush University Medical Center. It will exclude patients with a tracheostomy on admission, those requiring extracorporeal membrane oxygenation (ECMO), or transferred from an outside facility receiving more than 24 hours of mechanical ventilation. Two groups will be randomly assigned via computer randomization. The comparison group will be placed on the CleanSweep™ Closed Suction System immediately after intubation or upon arrival to the MICU. ETTs will be cleaned with the balloon sweeping technology every time a respiratory therapist suctioning the patient. The standard group will be placed on the standard in-line suction device. Airway suctioning will be performed in both groups as per department policy (Catheter advanced until resistance is met and withdrawn slowly for a duration no longer than 15 seconds while applying negative pressure). Both groups will also receive a ventilator bundle that consists of head of bed elevation, ETT cuff pressure management, DVT prevention, daily sedation interruption and SBT, and oral care every 4 hours with chlorhexidine at 12pm (noon) and 12am midnight.

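### The primary outcome, time to first successful SBT, has no value or rule for patients who never pass one, and the t-test read literally compares only those who did

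*Combined protocol and SAP*

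**What the plan says.** Specific Aims sets the primary outcome: "The primary aim of this study is to evaluate the CleanSweep™ Closed Suction System on time to first successful SBT in mechanically ventilated patients". Plans for Data Analysis is the only analysis text. For this outcome and for length of ventilation it says "time to first successful SBT and length of mechanical ventilation outcomes will be compared using an independent T-test if the data is normally distributed". No test is named for data that are not normal.

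No section gives a time origin, a follow-up horizon, a censoring or competing-event rule, an analysis population, a missing-data rule, or a value for a patient who never passes an SBT.

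Eligibility does not remove such patients. Subject Population excludes patients under 18, those with a tracheostomy, those on ECMO, and "Transfer from outside hospital with more than 24 hours of mechanical ventilation". Experimental Design words the tracheostomy criterion as "exclude patients with a tracheostomy on admission", so a later one can occur on study. Nothing excludes patients likely to die before weaning.

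The sample size uses length of ventilation: "ventilation is approximately 6.3 days with a standard deviation of 3.64", with a 20% reduction as the effect.

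**The concern.** A t-test needs one number per patient. Someone who dies, has support withdrawn or is transferred before passing an SBT has no time to first success. The analyst must then drop that patient or invent a value. Dropping compares groups defined by an event after randomisation. Entering the time of death scores an early death as a fast success. Entering a long penalty time lets mortality drive the result. Because the plan fixes none of these, the choice may be made with outcomes in view, on the primary comparison.

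Length of ventilation differs slightly. A value does exist at death, but a short one may mean death rather than liberation.

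**Working it through.** **1. The plan's own figure.** Effect 0.20 × 6.3 = 1.26 days; 1.26/3.64 = 0.346. With two-sided alpha 0.05 (sidedness is not stated) and 80% power, n per arm = 2 × (2.80/0.346)² ≈ 131.0, rounded up to 132. That is within 3% of the stated 136. The rounded 0.35 gives 129. At 136 per arm and effect 0.346, power is 81.4%.

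**2. What the cited mortality shows.** The Introduction gives 59% simple weaners with 13% mortality, 26% difficult with 9%, and for the rest "the prolonged weaning group represented 14% of the group with a 32% mortality rate".
- 0.59 × 0.13 + 0.26 × 0.09 + 0.14 × 0.32 = 0.077 + 0.023 + 0.045 = 0.145.
- Simple weaners supply 0.077/0.145 = 53% of this. The Introduction defines difficult weaning by failure of the initial SBT, so simple weaners passed theirs and would have a primary-outcome value.
- The figures show that deaths occur. They are not the rate of death before a first pass.

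**3. Loss of numbers alone.** If an assumed share q has no SBT time and is dropped, with SD 3.64 in both arms, n = 136(1 − q) and power = Φ(0.346 × √(n/2) − 1.96).

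| q | n per arm | power |
|---|---|---|
| 5% | 129 | 79.5% |
| 10% | 122 | 77.3% |
| 14.5% | 116 | 75.2% |
| 20% | 109 | 72.3% |
| 30% | 95 | 66.6% |

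**4. Simulation with deaths.** Assumptions: the length-of-ventilation mean and SD stand in for SBT time (lognormal, mu 1.697, sigma 0.537; or Weibull, shape 1.79, scale 7.08); 136 per arm; 28-day horizon; constant death hazard. A device effect multiplies weaning time by 0.8. This also shrinks the device arm's SD, so the power for dropping is higher than in step 3.

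*Real 20% effect, hazard 0.03/day in both arms (17% vs 14% die first):*

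| Rule | Lognormal power | Weibull power |
|---|---|---|
| Non-passers dropped, t-test | 81–82% | 77% |
| Time of death used, t-test | 76–77% | 75% |
| Log-rank | 83–84% | 84–85% |
| Worst-rank | 79–80% | 63% |

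The true 1.26-day gain appears as about 1.1 days when non-passers are dropped and 1.0 when time of death is used. For hazards from 0.01 to 0.05 (6% to 26% of controls die first; lognormal), dropping gives 87% to 76% power and log-rank 86% to 81%.

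*No effect, equal hazards (0.03).* Each rule fixed in advance rejects in about 2.5% per side. Taking any significant result among dropping, time of death and a 28-day penalty rejects in 11–12% of trials, two-sided.

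*No effect, hazard 0.03 control vs 0.05 device (17% vs 26% die first).* False device wins, nominal 2.5%: dropped 6–7%, time of death 16–17%, log-rank about 3%. With fewer device deaths (0.02), dropping rejects against the device in 4–5% and time of death in about 8%; log-rank stays at 2.5–3.0%.

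**5. Limit of log-rank.** If slower weaners also die more and device deaths are higher (23% vs 27%, then 23% vs 32%), false device wins are 5.5% and 12.3% for log-rank, 7.0% and 20.1% for dropping, and 13.4% and 48.0% for time of death. Worst-rank gives 0.9% and 0.5%, but rejects against the device in 5.2% and 12.2%.

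**The case against.** The strongest reply is that the most natural reading, a t-test on observed times, loses little: 81–82% power against 83–84% for log-rank in the main case, still above the planned 80%. That stands for power.

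Three further points also stand. First SBT success normally comes before ventilation ends, and both arms get daily SBTs, so a 6.3-day mean probably overstates exposure to death. At hazard 0.03, 17% die first with a mean of 6.3 days, but about 11% at an assumed 4 days and 9% at 3 days. The false-win results need death rates that differ by arm, which the documents do not suggest. And the choice between log-rank and worst-rank is partly a choice of estimand; the defect itself requires only one pre-stated rule.

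Stronger readings are tempting but unsupported:
- A reader might infer that power collapses. A 28-day penalty analysed by t-test does cut it to about 36%, but the documents mention neither a penalty nor a horizon.
- A reader might infer that a t-test can never include these patients. It can if a value is assigned; the plan assigns none.
- A reader might infer that about 14.5% will lack an outcome. More than half of that figure comes from patients who passed.
- A reader might infer that skew invalidates the t-test. At 136 per arm its two-sided error without deaths is 4.9% (lognormal) or 5.1% (Weibull). The missing fallback test is a pre-specification gap only.

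**Conclusion.** The concern holds as a gap in the primary analysis that must be closed before outcomes are seen by arm. The plan defines no outcome value or rule for patients who never pass an SBT, such patients are foreseeable, and the only named test, applied literally, compares a subset selected after randomisation.

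The power loss from dropping is modest under the stated assumptions. The more serious exposure is the undefined choice of rule: about 12% two-sided error if it is made after outcomes are known, even with equal deaths. Bias from a rule fixed in advance arises only if deaths differ by arm. Confidence is high for the omission. The size cannot be settled from the documents, which give neither the rate of death before a first pass nor any difference by arm.

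**What to change.** In Plans for Data Analysis, replace the t-test sentence with one primary analysis of all randomised patients by assigned arm, from randomisation to a stated horizon. Count first successful SBT as the event and death before it as a competing event. Use a two-sided log-rank test at 0.05 with a cause-specific hazard ratio and 95% CI, and show cumulative incidence of success and of death by arm. Analyse liberation from ventilation alive in the same way.

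State beside this choice that log-rank can favour the device if slower weaners die more and device deaths are higher, and add a worst-rank (Mann-Whitney) sensitivity analysis. Before outcomes are seen by arm, state how withdrawal of support, transfer and later tracheostomy enter the analysis.

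Restate the power of 272 patients for the chosen test under a time distribution consistent with the plan's mean and SD. For log-rank, as an illustration, it is 88% (lognormal) or 90% (Weibull) without deaths, and about 84% or 85% at a death hazard of 0.03/day.

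The cost is a short amendment, vital status and a few chart-derived dates, and an effect reported as a hazard ratio and curves rather than a difference in mean days.

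### Does the conditional t-test, with no normality criterion and no named fallback, leave the main comparison unsound?

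*Combined protocol and SAP*

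**What the plan says.** The Specific Aims make the primary aim to "evaluate the CleanSweep™ Closed Suction System on time to first successful SBT in mechanically ventilated patients". Length of mechanical ventilation is among the secondary aims.

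One sentence in Plans for Data Analysis covers both of these, which "will be compared using an independent T-test if the data is normally distributed". The only other test named is a chi-square test, for the ventilator-associated event rates. The significance level is 0.05; sidedness is not stated, and two-sided is assumed here.

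The sample size in the same section concerns length of ventilation: "ventilation is approximately 6.3 days with a standard deviation of 3.64", and "Effect is estimated at a 20% reduction in the length of mechanical ventilation", that is 1.26 days. It concludes: "Setting alpha at 0.05 and power of .80 with standardized effect size of 0.35 would require 136 patients in each group". No mean, SD or effect is given for time to first successful SBT.

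**The concern.** A test that applies only under a condition needs a way to judge the condition and an instruction for when it fails. The plan has neither, and for length of ventilation the condition will probably fail. Read literally, the primary comparison could then have no specified test.

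Three things would be at stake. First, two common readings of normality can send the same data down different routes. Second, the t-test and a rank test can fall on opposite sides of 0.05, and an analyst free to choose after seeing both could raise the false-positive rate. Third, the two tests address different quantities: the sample size rests on a difference in means, which a rank test does not estimate.

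**Working it through.** **Inputs.** From Plans for Data Analysis: mean 6.3 days, SD 3.64, reduction 1.26 days, alpha 0.05, power 0.80, 136 per group. Assumed: two-sided tests and the distribution shapes below.

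**1. The plan's sample size.** d = 1.26/3.64 = 0.346. With n per group = 2(1.960 + 0.842)²/d², this gives 15.70/0.1198 = 131.0, so 132; the t-based figure is 131.98, also 132. That is within 3% of 136. With d rounded to 0.35, the t-based figure is 129.1, so 130. Multiplying 129.1 by π/3, the allowance for a rank-sum test on normal data, gives 135.2, so 136. The exact match may hint at a rank-test sizing, but the plan does not say so. Either way 136 per group is adequate: t-test power at d = 0.346 is 81%.

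**2. Is normality plausible?** P(X < 0) = Φ(−6.3/3.64) = Φ(−1.731) = 0.042. Durations cannot be negative, so exact normality does not hold.

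**3. Which route would be taken?** Simulations used 20,000 trials per shape, 136 per arm, each shape with mean 6.3 and SD 3.64.

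| | Lognormal | Gamma | Weibull | Truncated normal | Uniform |
|---|---|---|---|---|---|
| Shapiro-Wilk rejects in at least one arm | 100% | 100% | 100% | 99.1% | 100% |
| Absolute skewness below 1 in both arms | 0.6% | 19.4% | 74.5% | 99.0% | 100% |

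The route does depend on the unwritten criterion.

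**4. Does the route matter for type I error?**

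| | Lognormal | Gamma | Weibull | Truncated normal | Uniform |
|---|---|---|---|---|---|
| t-test always | 5.1% | 5.1% | 5.0% | 4.8% | 5.0% |
| Shapiro-Wilk, then rank-sum | 4.9% | 5.1% | 5.0% | 4.8% | 5.0% |
| Smaller p of the two | 7.1% | 6.6% | 6.3% | 5.7% | 5.3% |

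A separate run of 10,000 trials on normal, lognormal and gamma data put the t-test at 4.4% to 5.5% and the rank-sum test at 4.8% to 5.2%.

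**5. Does the route matter for power?** Two effect models are reasonable. Under a fixed shift of 1.26 days both arms keep the SD of 3.64, as in the plan's sample size. Under a 20% proportional reduction the treated arm's SD also shrinks, to 0.8 × 3.64 = 2.91, which raises t-test power.

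| | Lognormal | Gamma | Weibull | Truncated normal | Uniform |
|---|---|---|---|---|---|
| Fixed shift: t-test | 80.6% | 81.1% | 81.6% | 81.3% | 81.2% |
| Fixed shift: rank-sum | 95.5% | 88.6% | 84.1% | 79.6% | 78.2% |
| Fixed shift: verdicts differ | 15.2% | 9.1% | 6.2% | 5.1% | 3.2% |
| 20% reduction: t-test | 88.6% | 88.3% | 88.8% | 88.7% | 88.2% |
| 20% reduction: rank-sum | 91.4% | 84.2% | 81.3% | 80.1% | 81.8% |
| 20% reduction: verdicts differ | 6.9% | 6.8% | 8.4% | 8.7% | 6.5% |

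The rank-sum test ranges from 95.5 − 80.6 = 14.9 points better to 88.7 − 80.1 = 8.6 points worse. Neither effect model is clean: a pure shift makes some short durations negative.

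**6. Time to first successful SBT.** The plan gives no spread, so lognormal data with a coefficient of variation of 1.0, 1.5 or 2.0 were assumed, with a 20% reduction.

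| Coefficient of variation | 1.0 | 1.5 | 2.0 |
|---|---|---|---|
| Welch type I error | 4.8% | 4.6% | 4.3% |
| Welch power | 46.6% | 25.1% | 17.0% |
| Rank-sum power | 57.4% | 37.6% | 29.2% |
| Verdicts differ | 22.1% | 23.9% | 22.5% |

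Welch keeps its level but is the weaker test here, by about 11 to 12.5 points.

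**The case for a change.** The strongest case for a change is that the unwritten branch is the likely one. The plan's own figures rule out exact normality, a formal test would almost always reject it, and nothing then says what to do. A rank-sum test is the usual substitute, but a t-test on the log scale is just as ordinary. Taking the best of three tests gives a type I error of about 7.1% (lognormal) or 7.6% (gamma). The verdict can turn on the choice, most of all under heavy skew, and a single sentence written before the data are seen would settle it.

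The factual part stands: the criterion and the fallback are missing, and neither redaction nor text extraction explains that. What does not stand is the step from there to an unsound result. The inflation needs someone to choose by p-value, which nothing in the plan suggests. Disagreement between two tests is not an error rate: each holds about 5%, and the disagreement mostly reflects their different power.

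Nor is there a clearly better single rule to put in. Making the Welch t-test unconditional can be defended as matching the sample size, but that calculation concerns length of ventilation. It says nothing about time to first successful SBT, where the t-test was the weaker one under the skew assumed. A mean difference in that outcome also has no definition for patients who never pass an SBT until their handling is settled, which is a separate matter. The point about different target quantities is fair, but the mean difference can be reported whichever test supplies the p-value.

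**Conclusion.** No change to the plan follows. This is a missing detail that a competent analyst would fill in the usual way: the t-test where its condition is judged to hold, and a rank-sum test otherwise. Both the t-test alone and the Shapiro-Wilk-then-rank-sum rule gave type I error between 4.8% and 5.1% at 136 per arm under the five shapes tried. The excess, up to 7.1% with two tests, needs selective choice that the plan does not describe. Replacing the condition with one fixed test trades power in one setting for power in another: the rank-sum test runs from about 15 points better to about 9 points worse for length of ventilation, and 11 to 12.5 points better in the skewed cases assumed for the primary outcome.

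This rests on two-sided tests and on assumed shapes. The mean and SD apply to length of ventilation only, and the spread for time to first successful SBT is an assumption. The simulations leave out deaths and patients who never pass an SBT.
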